3.2 END OF STUDY AND LENGTH OF STUDY

3.2.1 End of Study

The primary analysis will take place at the earliest timepoint when all randomized patients (Arms A, B, and C) have either completed at least 24 weeks of treatment or discontinued from the study. For Arm D, the primary efficacy analysis will be conducted after the last enrolled patient have completed at least 24 weeks in the study or discontinued from treatment.

Patients who discontinue study treatment prior to end of study (with the exception where the reason for discontinuation is the patient switching to commercial emicizumab product) will return to the clinic for a safety follow-up visit 24 weeks after the final dose of study drug.

The end of this study is defined as the date when the last remaining patient has completed the last visit (LPLV), as defined by any of the following criteria:

- Completion of at least 24 weeks of emicizumab treatment
- Completion of safety follow-up visit 24 weeks after discontinuing emicizumab
- Completion of the study Extension Phase (*3 years after the last Arm D patient completes 1 year treatment and patients still having clinical benefit are transferred to a post-trial continued access solution per Roche Global Policy on Continued Access to Investigational Medicinal Products [see Section 4.3.4]*)
- Withdrawal of consent
- Lost to follow-up

The study will end earlier, before 3 years after the last Arm D patient completes 1 year treatment, should the post-trial continued access solution be available earlier.

3.2.2 Length of Study

The length of the study for an individual patient will be:

- Screening period up to 4 weeks
- Treatment and observation period at least 24 weeks
- Safety follow-up visit 24 weeks after discontinuing emicizumab
- An extension phase in this study for all patients who complete at least 52 weeks of treatment with prophylactic emicizumab and still deriving clinical benefit for 3 years after last Arm D patient completes 1 year of treatment. *Extension phase may end earlier, before 3 years after the last Arm D patient completes 1 year treatment, should a post-trial continued access solution be available earlier.*

The approximate length of the entire study from screening of the first patient to the end of the study (including Arm D and study Extension Phase) will be approximately 88 months.

3.3 RATIONALE FOR STUDY DESIGN

This is a multicenter, open-label, Phase III clinical study with randomized and non-randomized arms. Patients aged 12 years or older with hemophilia A with or without inhibitors against FVIII will be randomized to receive one of the following regimens:

- Emicizumab prophylaxis at 3 mg/kg QW for 4 weeks, followed by 1.5 mg/kg QW subcutaneously (Arm A)
- Emicizumab prophylaxis at 3 mg/kg QW for 4 weeks, followed by 6 mg/kg Q4W subcutaneously (Arm B)
- No prophylaxis control arm (Arm C)

Patients aged <12 years with hemophilia A with inhibitors against FVIII will be enrolled to receive the following regimen:

- Emicizumab prophylaxis at 3 mg/kg QW for 4 weeks, followed by 1.5 mg/kg QW subcutaneously (Arm D)

This prospective, randomized design (Arms A, B, and C) allows uniform collection of bleed data, medication use, and patient-reported outcomes (PROs) through the use of patient-validated measurement tools in all groups, enabling analysis of the effect of prophylactic emicizumab versus episodic therapy on these important measures.

Reporting of bleeds by patients to their providers (e.g., doctors, nurses) is not standardized and can be incomplete in routine clinical care. In addition, the recording of bleeds by providers in medical records may be inconsistent. Therefore, testing the primary endpoint using a prospective randomized design is superior to comparison to historical control in patients who were not on prophylaxis prior to enrollment.

Given the proven efficacy of prophylaxis, it can be expected that standard-of-care may evolve towards more widespread treatment of patients with prophylaxis regimens. However, for myriad reasons, currently only about half the patients in developed countries and less than 20% patients in China are managed with routine prophylaxis, making the episodic approach a commonly used standard care (Richards et al. 2007; Xue et al. 2011; Gringeri et al. 2012; Zappa et al. 2012; Jackson et al. 2014; Oldenburg and Brackmann 2014; Jackson et al. 2015; Oldenburg 2015). Thus, for the primary efficacy endpoint, patients with no prophylactic therapy will be compared with patients treated with prophylactic emicizumab. This study will only enroll patients who previously received episodic therapy; this approach will reduce heterogeneity in the study population, which is appropriate since the bleed rates for patients receiving therapy on an episodic versus prophylactic basis are significantly different (Valentino et al. 2012; Manco-Johnson et al. 2013; Powell et al. 2013; Antunes et al. 2014; Mahlangu et al. 2014; Windyga et al. 2014). To help balance measured and unmeasured covariates between the groups with prophylactic emicizumab and the control group with no prophylactic therapy, randomized patients will be stratified according to the number of bleeds they had over the 24 weeks prior to study entry (less than versus greater than or equal to 9 bleeds).

The primary efficacy analysis to assess the effect of emicizumab on bleed rate reduction will be performed at the earliest timepoint when all randomized patients have either completed 24 weeks of study treatment or discontinued from the study. Indeed, a similar follow-up period was used in recent studies that investigated the safety and efficacy of novel FVIII formulations and in the emicizumab global studies (Mahlangu et al. 2014; Kavakli et al. 2015; Konkle et al. 2015). Further, patients who experience frequent bleeds may not find it acceptable to be randomized to their usual episodic therapy for longer than 24 weeks prior to receiving emicizumab. For this reason, individual patients in the control arm will be offered the opportunity to switch to emicizumab after 24 weeks in the study.

With available PK, efficacy, and safety data of emicizumab prophylaxis treatment in pediatric inhibitor patients, the effect of bleeding control is regardless of age, prior treatment choice, and bleeding history. Thus, Arm D has been added to enroll pediatric patients with no limitation in terms of the minimal age; patients with both prior episodic and prophylaxis treatment with bypassing agents are allowed.

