3. STUDY DESIGN

3.1 DESCRIPTION OF THE STUDY

Study YO39309 is a multicenter, open-label, Phase III clinical study with randomized and non-randomized arms designed to investigate the efficacy, safety, and pharmacokinetics of emicizumab in patients with hemophilia A regardless of FVIII inhibitor status.

Seventy patients aged ≥ 12 years who received episodic therapy with FVIII or bypassing agents prior to study entry and experienced at least 5 bleeds over the prior 24 weeks will be randomized in a 2:2:1 ratio (see [Figure 1](#)) to the following regimens:

- Arm A: Emicizumab prophylaxis at 3 mg/kg QW subcutaneously for 4 weeks, followed by 1.5 mg/kg QW subcutaneously
- Arm B: Emicizumab prophylaxis at 3 mg/kg QW subcutaneously for 4 weeks, followed by 6 mg/kg Q4W subcutaneously

- Arm C: No prophylaxis (control arm)

In addition, 15 pediatric patients with hemophilia A and inhibitors who received episodic therapy with bypassing agents prior to study entry will be enrolled to Arm D:

- Arm D: Emicizumab prophylaxis at 3 mg/kg QW subcutaneously for 4 weeks, followed by 1.5 mg/kg QW subcutaneously

The endpoints will be analyzed separately for the two randomized emicizumab arms (Arms A and B): 1.5 mg/kg QW and 6 mg/kg Q4W, as well as for the additional arm in pediatric patients (Arm D): 1.5 mg/kg QW.

Randomized patients will be stratified according to the number of bleeds the patient experienced over the 24 weeks prior to study entry—less than versus greater than or equal to 9—to ensure a balance of patients with lower versus higher number of bleeds in all arms.

To ensure a representative variety of patients with hemophilia A enrolled in this study to investigate the efficacy and safety profile of emicizumab in both inhibitor and non-inhibitor adolescent and adult populations, enrollment of up to 55 non-inhibitor patients will be permitted.

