4. MATERIALS AND METHODS

4.1 PATIENTS

A total of 70 patients with severe hemophilia A who previously received episodic therapy with either FVIII or bypassing agents will be enrolled in Arms A, B, and C.

A total of 15 pediatric patients with hemophilia A with inhibitors from China mainland who previously received episodic therapy with bypassing agents will be enrolled in Arm D.

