Examples of contraceptive methods with a failure rate of $< 1\%$ per year include proper use of combined oral or injected hormonal contraceptives, bilateral tubal ligation, male sterilization, hormone-releasing intrauterine devices, and copper intrauterine devices. Alternatively, two methods (e.g., two barrier methods such as a condom and a cervical cap) may be combined to achieve a failure rate of $< 1\%$ per year. Barrier methods must always be supplemented with the use of a non-lipid-based spermicide.

The reliability of sexual abstinence should be evaluated in relation to the duration of the clinical study and the preferred and usual lifestyle of the patient. Periodic abstinence (e.g., calendar, ovulation, symptothermal, or postovulation methods) and withdrawal are not acceptable methods of contraception.

4.1.1.2 **Arm D**

Patients in Arm D must meet the following criteria for study entry:

- Written informed consent must be obtained from parent/legally acceptable representative and an assent from the child when applicable (latest approved version by the Independent Ethics Committee [IEC]/Institutional Review Board [IRB]) prior to any of the study-specific assessments and procedures being performed.
- Children < 12 years of age at time of informed consent
- Body weight $> 3 \text{ kg}$ at time of informed consent
- Willingness and ability to comply with scheduled visits, treatment plans, laboratory tests, and other study procedures, including the completion of applicable PRO questionnaires

- Caregivers of all children must have the willingness and ability to comply with all study procedures, including the completion of the bleed/medication questionnaire and applicable HRQoL questionnaires
- Diagnosis of congenital hemophilia A of any severity and documented history of high-titer inhibitor (i.e., ≥ 5 BU/mL)
- Requires treatment with bypassing agents
- Adequate hematologic function, defined as platelet count of $\geq 100 \times 10^9$ cells/L and hemoglobin ≥ 8 g/dL (4.97 mmol/L) at the time of screening
- Adequate hepatic function, defined as total bilirubin $\leq 1.5 \times$ age-adapted ULN (excluding Gilbert's syndrome) and both AST and ALT $\leq 3 \times$ age-adapted ULN at the time of screening
- Adequate renal function: serum creatinine must be $\leq 1.5 \times$ ULN for age

If serum creatinine is $\geq 1.5 \times$ ULN, creatinine clearance by Bedside Schwartz formula must be > 70 mL/min/1.73m².

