4.1.2.2 Arm D

Patients in Arm D who meet any of the following criteria will be excluded from study entry:

- Inherited or acquired bleeding disorder other than hemophilia A
- Ongoing (or plan to receive during the study) ITI therapy or prophylaxis treatment with FVIII
 - Patients awaiting initiation of ITI will be eligible.
 - Patients in whom ITI has failed will be eligible with a 72-hour washout period prior to the first emicizumab administration.
- Previous (in the past 12 months) or current treatment for thromboembolic disease (with the exception of previous catheter-associated thrombosis for which anti-thrombotic treatment is not currently ongoing) or signs of thromboembolic disease
- Other diseases (i.e., certain autoimmune diseases [e.g., systemic lupus erythematosus], cardiovascular disease) that may increase risk of bleeding or thrombosis
- History of clinically significant hypersensitivity associated with monoclonal antibody therapies or components of the emicizumab injection
- Known infection with HIV, hepatitis B virus (HBV), hepatitis C virus (HCV)
- Patients who are at high risk for thrombotic microangiopathy (e.g., have a previous medical or family history of thrombotic microangiopathy), in the investigator's judgment

- Use of systemic immunomodulators (e.g., interferon or corticosteroids) at enrollment or planned use during the study
- Planned surgery (excluding minor procedures such as tooth extraction or incision and drainage) during the study
- Inability (or unwillingness by caregiver) to receive (allow receipt of) blood or blood products (or any standard-of-care treatment for a life-threatening condition)
- Receipt of:
 - An investigational drug to treat or reduce the risk of hemophilic bleeds within 5 half-lives of last drug administration
 - A non-hemophilia-related investigational drug within last 30 days or 5 half-lives, whichever is shorter
 - An investigational drug concurrently
- Concurrent disease, treatment, or abnormality in clinical laboratory tests that could interfere with the conduct of the study or that would, in the opinion of the investigator or Sponsor, preclude the patient's safe participation in and completion of the study or interpretation of the study results
- Pregnant or lactating, or intending to become pregnant during the study
 - Female patients with a positive serum pregnancy test result within seven days prior to initiation of study drug.

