affecting the type 1 error rate. Study integrity will be upheld, as access to information via aggregated analyses and their results will be minimized to limit operational bias.

The sample size for Arm D is based on favorable recruitment feasibility and clinical considerations rather than statistical considerations, taking into account the limited number of pediatric patients with hemophilia A inhibitors available for participation. Hence, approximately 15 children < 12 years of age with hemophilia A and FVIII inhibitors who are currently receiving treatment with bypassing agents will be enrolled in this study.

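### The protocol gives two answers on whether a child with prior bypassing-agent prophylaxis may enter Arm D

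*Protocol*

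**What the plan says.** Restrictive statements. Section 3.1 describes the Arm D children as those "who received episodic therapy with bypassing agents prior to study entry will be enrolled to Arm D". Section 4.1 describes them as children "who previously received episodic therapy with bypassing agents will be enrolled in Arm D". The synopsis says the same in both its study description and its patient numbers. Section 3.3 adds a sentence about the study as a whole: "This study will only enroll patients who previously received episodic therapy; this approach will reduce heterogeneity in the study population". Its stated reason is that bleed rates differ significantly between episodic and prophylactic therapy.

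Permissive statement. Later in Section 3.3, in the paragraph explaining why Arm D was added, the protocol says that "patients with both prior episodic and prophylaxis treatment with bypassing agents are allowed".

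Formal criteria. The Arm D inclusion list (Section 4.1.1.2) says only "Requires treatment with bypassing agents". The relevant Arm D exclusion (Section 4.1.2.2) reads "Ongoing (or plan to receive during the study) ITI therapy or prophylaxis treatment with FVIII"; it does not mention bypassing-agent prophylaxis. Section 6.1 describes the children as those "who are currently receiving treatment with bypassing agents will be enrolled in this study", again without saying how the agents are used.

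Analysis. Table 2 lists change from the patient's historical bleed rate as a secondary endpoint for Arms A, B, C and D. Section 6 says that Arm D is descriptive, with no formal hypothesis test. The SAP is based on protocol version 3 and does not cover Arm D.

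**The concern.** An eligibility rule should have one reading. Section 9.2 forbids waivers of eligibility criteria, so a site or monitor has to know whether a child who was on bypassing-agent prophylaxis is a valid entry or a deviation. The current text supports either answer.

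There is also a limited analysis consequence. Arm D has no concurrent control, and one of its listed secondary endpoints compares on-study bleeding with the child's own past rate. Section 3.3 itself says that the past rate depends on whether earlier treatment was episodic or prophylactic. If both kinds of patient are admitted and the report describes the arm as previously episodic, the historical rate will be attributed to the wrong population. Neither document plans a split of Arm D by prior regimen.

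**Working it through.** There is no planned figure to reproduce: the protocol says that "The sample size for Arm D is based on favorable recruitment feasibility and clinical considerations rather than statistical considerations". The check is a comparison of texts, followed by an attempt to size the consequence.

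**1. The texts side by side**

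- Synopsis, Section 3.1, Section 4.1: prior episodic therapy.
- Section 3.3, study-wide sentence: prior episodic therapy only.
- Section 3.3, Arm D paragraph: prior episodic or prophylactic therapy.
- Sections 4.1.1.2, 4.1.2.2 and 6.1: bypassing agents required, mode of use not stated.
- Section 4.4.2: the bans on concomitant FVIII or rFVIIa prophylaxis and on short-term aPCC/PCC prophylaxis do not apply to the 4 weeks before study treatment, so they do not exclude prior use.

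Taken literally, the criteria admit a child with prior bypassing-agent prophylaxis. The conflict is therefore between the population descriptions on one side and the Arm D rationale and criteria on the other. No two listed criteria contradict each other.

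**2. Which analyses depend on prior regimen**

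- Arm D primary endpoint (Table 2): on-study number of treated bleeds over time. Needs no baseline.
- All, spontaneous, joint and target joint bleeds: on-study counts, also without a baseline rate.
- Change from historical bleed rate: uses the past rate. This is the one bleed endpoint affected.
- Section 6.4.2 describes the historical comparison for Arms A, B and C only and gives Arm D descriptive on-study analyses. The endpoint is thus listed for Arm D without a stated method.

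**3. Can the shift be sized?**

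Inputs, none of which is an Arm D figure:

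- ABR without prophylaxis: 18, the control-arm planning value in Section 6.1 for randomized patients aged 12 or older, who needed at least 5 bleeds in 24 weeks. Arm D has no minimum bleed count.
- ABR on bypassing agents (Section 1.1.1): 8 to 10 with aPCC, or 2 to 3 bleeds per month with rFVIIa, which is 24 to 36 per year. Treating both as rates on prophylaxis is an assumption.
- Number of children with prior prophylaxis, k: unknown.

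Mean historical ABR = ((15 − k) × 18 + k × P) / 15, where P is the ABR on prior prophylaxis.

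- k = 0: 18.0.
- k = 1, P = 8 to 10: (252 + 8)/15 = 17.3 to (252 + 10)/15 = 17.5.
- k = 1, P = 24 to 36: (252 + 24)/15 = 18.4 to (252 + 36)/15 = 19.2.
- k = 5, P = 8 to 10: (180 + 40)/15 = 14.7 to (180 + 50)/15 = 15.3.
- k = 5, P = 24 to 36: (180 + 120)/15 = 20.0 to (180 + 180)/15 = 24.0.

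The sign changes with the product assumed. Section 1.1.1 says that the products available in China are PCC and rFVIIa, and Arm D enrolls only from mainland China, so the aPCC figure has no special claim.

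**4. Effect on the reduction**

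The earlier pediatric inhibitor study (Section 1.2.2.2) had 22 treated bleeds in 65 participants over a median of 58 weeks. Approximating patient-time by the median, on-study ABR ≈ 22 / (65 × 58 / 52.18) = 0.30. The percent reduction is 1 − 0.30/18 = 98.3% if no child had prior prophylaxis. If all 15 did, at ABR 8 to 10, it is 96.2% to 97.0%. The absolute reduction goes from 17.7 to between 7.7 and 9.7 bleeds per year. At an on-study ABR of 4, the planning value, the percent reduction would go from 77.8% to between 50.0% and 60.0%.

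**The case against.** The strongest defence is that Sections 4.1.1.2 and 4.1.2.2 govern entry, and they are clear enough. They contain no episodic-only rule, whereas Section 4.1.1.1 does require documented episodic therapy for Arms A to C. The study-wide sentence in Section 3.3 sits in the rationale for the randomized comparison and may simply predate Arm D. This stands in part: it shows that the criteria and the Arm D rationale agree. It does not remove the synopsis, Section 3.1 and Section 4.1, which speak of Arm D by name and say episodic.

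A reader might go further and infer that Arm D's bleed results as a whole are judged against history and become uninterpretable. The documents do not support that. Only one descriptive secondary endpoint uses history, and it compares each child with himself. Section 1.2.2.2 already reports a pooled result of this kind: a 99% reduction in 18 children with prior episodic or prophylactic treatment.

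A reader might also infer that prior prophylaxis would pull the mean historical ABR down from 18 to about 15. That needs the aPCC figure, a planning value from older patients, and five such children out of 15. Section 1.1.1 reports that prophylaxis is very rare among inhibitor patients in China, and its rFVIIa figure would push the mean up.

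Finally, prior regimen cannot be assumed to be on file. Section 4.5.2 collects medications from 4 weeks before screening and the number of bleeds over 24 weeks. No Arm D criterion requires 24 weeks of treatment documentation.

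**Conclusion.** Wrong as written, and minor. The current protocol text gives two answers on who may enter Arm D, and the formal criteria side with the permissive one without saying so. The consequence is confined to the eligibility status of individual children, each about 7% of the arm (1/15), and to the reading of change from historical bleed rate. The randomized comparisons, their alpha and power, and Arm D's primary endpoint do not depend on this.

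No numerical bias can be claimed. The figures above are illustrations resting on rates from other populations and an unknown number of children; they show only that neither the size nor the direction of a baseline shift can be obtained from the documents. The documents do not show that sites applied different rules, and they do not say whether Arm D enrollment is still open.

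**What to change.** Reconcile the synopsis, Section 3.1, both statements in Section 3.3, and Section 4.1, and state the resulting rule on prior bypassing-agent prophylaxis explicitly in Section 4.1.1.2. Which rule applies is for the sponsor to decide.

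If both prior regimens are or were admitted, list each Arm D child's historical bleed rate and change from it by prior regimen. Confirm prior regimen from medical records where it was not collected. If enrollment is complete, this listing is the part that still helps the reader.

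The cost is protocol wording, one listing in which one group may hold very few children, and possibly a record check at sites.

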3.3.1 Rationale for Emicizumab Dose and Schedule

Emicizumab prophylaxis has been administered subcutaneously in 18 Japanese patients with hemophilia A (with and without FVIII inhibitors) in Study ACE001JP and in its extension Phase I/II Study ACE002JP. Three dose groups (of 6 patients each) received the following treatment (administration period of 12 weeks):

- A loading dose of 1 mg/kg followed by weekly doses of 0.3 mg/kg
- A loading dose of 3 mg/kg followed by weekly doses of 1 mg/kg
- Weekly doses of 3 mg/kg

Emicizumab was safe and well tolerated in these patients (see Section 1.2.2 and the Emicizumab Investigator's Brochure). The maximum clinical dose of 3 mg/kg/week is associated with a 10.3-fold and 11.2-fold safety margin based on C_{max} and AUC_{τ} , respectively. No clear difference in the plasma concentrations of emicizumab was observed between adolescents (12–18 years) and adult (aged 19–58 years) patients.

A substantial reduction in bleeding events has been observed with prophylactic emicizumab treatment, especially at doses ≥ 1 mg/kg/week (see Table 3, based on data cutoff of 17 April 2015). ABR decreased in all patients, regardless of age or the presence of FVIII inhibitors.

[figure not shown]
Table 3 Mean Reduction (%) of Annualized Bleeding Rates in Inhibitor and Non-Inhibitor Patients Enrolled in Study ACE001JP/ACE002JP

Emicizumab Dose	0.3 mg/kg/wk	1 mg/kg/wk	3 mg/kg/wk
ABR reduction	74.5%	95.3%	96.4%

ABR = annualized bleeding rate; wk = week.

A median ABR of 0 was achieved with weekly maintenance doses of 1 and 3 mg/kg. The number of bleeding events decreased with increased emicizumab plasma concentrations (see [Figure 2](#)).

Figure 2 Individual Pharmacokinetic Profile with Corresponding Bleeding Event

0.05 ug/mL was assigned if below the lower limit of quantification.
 Filled and open circles represent the predicted values of analyte at the beginning time of each bleeding episode required coagulation factor treatment including and not including joint bleeding, respectively.
 Predicted value was obtained based on linear interpolation between previous and next observed values around the beginning time of each bleeding episode, or last observation carried forward if bleeding episode occurred after the last observed time of analyte included in the analysis.
 Datetime: June 8, 2015 14:59:00

ACE910 = emicizumab (also known as RO5534262)

[figure not shown]
● Joint bleed

○ Non-joint bleed

The exposure-response relationship of emicizumab was quantitatively characterized and simulations suggested that a median ABR of 0 is achieved for emicizumab trough plasma $\geq 45 \mu\text{g/mL}$. On the basis of population PK modeling, a median trough plasma concentration of $45 \mu\text{g/mL}$ is predicted to be achieved after one month of treatment with 4 weekly doses of 3 mg/kg and maintained, thereafter, with either weekly doses of 1.5 mg/kg or biweekly doses of 3 mg/kg .

A dose of 6 mg/kg Q4W is equivalent in terms of cumulative dose to the dose levels of 1.5 mg QW or 3 mg/kg Q2W that are being evaluated in the other Phase III studies. Assuming linear pharmacokinetics up to 6 mg/kg , model-based simulations were used to explore whether a Q4W dosing regimen could provide sufficient efficacy. Simulations showed that a once-weekly loading dose of 3 mg/kg for the first 4 weeks, followed by an every 4-week maintenance dose of 6 mg/kg would provide a steady-state C_{\max} and AUC_{τ} of $78.1 \pm 20.9 \mu\text{g/mL}$ and $1570 \pm 447 \text{ day}\cdot\mu\text{g/mL}$, respectively (see [Figure 3](#)). While more than half of the patients would not be expected to have a trough level of $\geq 45 \mu\text{g/mL}$ at steady state, the simulated ABR distribution was similar to the planned dosing regimens of other Phase III studies. Therefore, this Q4W dosing regimen is expected to maintain similar efficacy to the QW and Q2W dosing regimens.

Figure 3 Simulated Plasma Emicizumab Concentration over Time (Q4W Dosing)

Q4W = every 4 weeks; RO5534262 = emicizumab.

Dots and solid line = simulated median plotted at each trough sampling timepoint.

Shaded area = simulated 5- to 95-percentile range.

Broken line = target exposure level of 45 µg/mL.

NOTE: Once-weekly loading dose of 3 mg/kg for first 4 weeks followed by every 4 weeks maintenance dose of 6 mg/kg was applied.

Overall, a Q4W dosing regimen with 6 mg/kg is expected to provide favorable safety and efficacy in patients with hemophilia A with or without inhibitors. A global Study BO39182 is planned to investigate the efficacy, safety, and pharmacokinetics of Q4W SC administration of emicizumab. It is estimated that the study results of BO39182 will be available before the initiation of Study YO39309. A re-assessment of Q4W dosing schedule based on the results of BO39182 will be performed.

The loading doses of 3 mg/kg QW for 4 weeks were chosen in order to rapidly achieve the effective trough concentration of 45 µg/mL without exceeding the maximum dose of 3 mg/kg QW investigated in the Phase I and Phase I/II studies. The two maintenance dosing regimens will offer flexibility of dosing frequency to patients. Therefore, these prophylaxis regimens (i.e., 3 mg/kg QW for 4 weeks followed by 1.5 mg/kg QW or 6 mg/kg Q4W) will be investigated in this study.

Due to the similarity of the disease between adults/adolescents and children, as well as the availability of a physiologically functioning coagulation system from 6 months onwards (including the targets of emicizumab, FIX and FX), there are no anticipated differences in the action of emicizumab in pediatric patients compared with adults. Indeed, pediatric and adult patients with hemophilia A have shown a similar response to treatment with FVIII compounds (Mahlangu et al. 2014; Young et al. 2015) and bypassing agents (Young et al. 2012). In the Japanese Phase I/II clinical studies with emicizumab, adolescent patients (aged 12–18 years) with hemophilia A have demonstrated similar safety and efficacy results to those observed in adults. Furthermore, in the Phase III HAVEN 2 study, enrolling pediatric (<12 years of age) hemophilia A patients with inhibitors, no effects of age on PK parameters were found. Given emicizumab PK characteristics and analysis of patient characteristics, no dose adjustment appears to be required for specific patient populations (i.e., children, adolescents, the elderly, or patients with renal or hepatic impairment). Therefore, the dosing regimen to be investigated in the present study in patients <12 years of age is to be selected to target a similar plasma emicizumab concentration trough level as the one being targeted in adolescents and adults (i.e., 45 µg/mL).

